5.1.2 Phase II

The phase II portion will consist of patients with ES-SCLC who completed platinum based standard first-line chemotherapy (e.g. 4-6 cycles of platinum plus etoposide or irinotecan) without disease progression (responders plus stable disease) at the time of initiation of the combination therapy with $^{177}\text{Lu-DOTA}^0\text{-Tyr}^3\text{-Octreotate}$ and nivolumab. Eligible patients will then be randomly allocated in two arms: one will be treated with the combination of $^{177}\text{Lu-DOTA}^0\text{-Tyr}^3\text{-}$

Octreotate and nivolumab, and the other arm will continue be followed (observation) after completion the standard chemotherapy treatment.

Randomization:

Patients who do not receive radiotherapy after chemotherapy

- The randomization must occur within 6 weeks of the last chemotherapy cycle.
- The study treatment must start within 2 weeks from randomization, but no less than 2 weeks from last dose of chemotherapy.

Patients who receive radiotherapy (including prophylactic cranial radiation and/or thoracic radiation) after chemotherapy

- Randomization must occur at least 8 weeks after completion of radiation therapy but within 12 weeks after completion of radiation therapy.

Randomization process:

- OnCore will be used as statistical center and the randomization algorithm will be developed by the study biostatistician.
- The project management department will be the first point of contact for assessment through email.

Courses are defined as 56 days of dosing. Nivolumab will be given until progressive disease, patient withdrawal, or toxicities. For patients randomized to the observation group, cross-over at the time of disease progression will be allowed, since the primary endpoint is PFS and not OS.

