2.1.2 Treatment for SCLC

Treatment options for SCLC are limited. Platinum-based chemotherapy regimens have been the standard of care for a long time [6]. While the combination of platinum-based chemotherapy and thoracic radiotherapy (RT) for limited-stage SCLC produces response rates close to 90%, the duration of response is relative short, and most patients relapse after completion of treatment, although approximately 20% of patients can be cured with concomitant chemo-radiation [7, 8]. For patients with ES-SCLC, chemotherapy is the mainstay of treatment, but objective response rates (ORRs) are lower at 45-60%, with infrequent complete responses and median PFS and OS of around 5 months and 10 months, respectively [9, 10]. Second-line chemotherapy for the treatment of relapsed SCLC is less effective than the initial treatment. Topotecan is the only drug that was approved by the US Food and Drug Administration (FDA) for the treatment of relapsed SCLC in 1996 [11]. Topotecan yields objective response rates of 20-24% [12, 13]. The response rate in patients refractory to prior chemotherapy (6%) is lower than (37%) in those sensitive to first-line chemotherapy [12]. Prognosis for patients with relapsed SCLC is grim with a median overall survival of 5.4 months [12]. There is an urgent need to develop more effective therapies for patients with SCLC.

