11.2 Sample Size and Accrual

ES-SCLC (i.e. SCLC that has spread beyond the supraclavicular areas or with distant metastases) remains incurable with current management options, and patients are treated with combination chemotherapy. Several chemotherapy combinations are active in SCLC, but usually a platinum-containing regimen is chosen. The ORR of platinum-based therapy administered to patients with ES-SCLC ranges from 40 to 80%, and the median PFS ranges from 5 to 7 months in patient series treated in a clinical trial setting (phase-II/III studies) [9, 10, 48-55]. A placebo-controlled randomized phase II study of maintenance sunitinib shows that median PFS was 2.1 months in the placebo group[56].

Based on historic average clinical outcomes, we propose a clinical study that will be integrated by a dose finding approach followed by a randomized phase II study with PFS as the primary endpoint, designed to have 80% power for a two-sided 0.05 level test. The completion of the first part of the study will require approximately 8-9 months for accrual assuming 9 to 12 patients will be required for the completion of the phase I portion with the participation of 7 institutions (Georgetown Lombardi comprehensive Cancer Center, Memorial Sloan Kettering Cancer Center, University of California, Los Angeles, University of California, San Francisco, Vanderbilt University, Hackensack University Medical Center, and Walter Reed National Military Medical Center).

For the phase II portion, assuming a median PFS of 2 months following completion of first-line therapy with a platinum-based chemotherapy for ES-SCLC in the control arm, and an expected median PFS of 5 months for the maintenance therapy with $^{177}\text{Lu-DOTA}^0\text{-Tyr}^3\text{-Octreotate}$ and nivolumab in the experimental arm (hazard ratio 0.4), it will be required to document 40 PFS events from a total population of 44 patients enrolled during a period of 18 month, including a minimum follow up of 10 months, with an expected accrual rate of 3-4 patients per month and the participation of 6-7 institutions. Assuming a potential 15% dropout, the total number of patients to recruit will be 52 [57-59].

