11.3 Data Analyses Plans

PFS will be defined as the time from random assignment to disease progression or death from any cause, whichever comes first. OS will be defined as the time from random assignment to death from any cause; living patients will be censored at the date of last follow-up. Survival will be estimated and plotted by the Kaplan–Meier method. In addition, the median progression-free and overall survival times will be reported along with the 95% confidence intervals. The cox proportional hazards regression model will be used to obtain hazard ratios (HRs) and the log-rank test will be utilized to compare survival estimates between the maintenance group and the control observation group. Secondary endpoints will be analyzed when the required number of events for the primary endpoint (PFS) has been met. The DCR is defined as the proportion of patients with a best overall response of CR, PR, or SD. The ORR is defined as the proportion of patients with a best overall response of CR or PR. All randomized subjects will consist of the safety population. This population will be used for all summaries of safety data (AEs, concomitant medications, laboratory data). P-values less than 0.05 will be considered significant. All statistical analyses will be performed using SAS (Version 9.4; SAS Institute, Cary, NC). [name] will serve as the study statistician.

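### Phase II names no stratification factor and plans an unstratified PFS analysis, although patients given post-chemotherapy radiotherapy enter later and after a longer progression-free wait; stratifying on that one factor is a cheap improvement

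*Combined protocol and SAP*

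**What the plan says.** **Randomization.** Section 5.1.2 allocates phase II patients to two arms and states that "the randomization algorithm will be developed by the study biostatistician". It gives no allocation ratio, block scheme, minimization rule or stratification factor, and no other section does.

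**Entry windows.** Patients without radiotherapy after chemotherapy are randomized no later than 6 weeks after the last cycle. For those who receive it, "Randomization must occur at least 8 weeks after completion of radiation therapy but within 12 weeks after completion of radiation therapy". Section 4.2.1.5 repeats both windows, and 4.2.1.1 requires that no patient has progressed before randomization. Section 4.2.1.4, however, asks for only 2 weeks or more between prior radiotherapy and randomization, and its wording covers cranial and thoracic radiation too.

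**Analysis.** Under section 11.3, "the log-rank test will be utilized to compare survival estimates between the maintenance group and the control observation group". A Cox model supplies the hazard ratio. No strata or covariates are mentioned for either.

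**Design.** Section 11.2 describes a trial "designed to have 80% power for a two-sided 0.05 level test", with 40 events from 44 patients, raised to 52 for 15% dropout.

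**The concern.** PFS runs from randomization. A patient who has had post-chemotherapy radiotherapy reaches that point only after 8 to 12 further weeks without progression. The design is built "assuming a median PFS of 2 months following completion of first-line therapy" in the control arm, so the shortest permitted wait (8 weeks, about 1.8 months) is about as long as the whole assumed control median. The protocol therefore creates a subgroup already filtered for slower disease, and it is plausible that this subgroup has longer PFS from time zero in either arm.

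Two things are at stake in a trial of 52. The subgroup may split unevenly between arms by chance and move the estimated hazard ratio. And an analysis that leaves out a strong prognostic factor has less power than one that uses it. The factor is known at entry, so both can be dealt with at almost no cost before the first phase II patient, whereas a chance imbalance cannot be undone afterwards.

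**Working it through.** **Inputs from section 11.2.** Two-sided 0.05 and 80% power; control median 2 months; "an expected median PFS of 5 months for the maintenance therapy"; "hazard ratio 0.4"; 40 events; 44 patients, 52 after dropout. **Assumptions, because the documents are silent:** 1:1 allocation, prevalence of the factor, and its prognostic HR (worse against better group).

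**1. The plan's own figures.**
- Schoenfeld: 4(1.960 + 0.842)²/(ln 0.4)² = 31.4/0.840 = 37.4, so 38 events.
- Freedman: (1.960 + 0.842)² × (1.4/0.6)² = 42.7, so 43 events. The stated 40 lies between the two.
- Power at 40 events (Schoenfeld): Φ(0.916 × √40/2 − 1.960) = Φ(0.938) = 82.6%; by Freedman 77.4%.
- Recruitment: 44/0.85 = 51.8, so 52. The design reproduces.

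**2. Chance of imbalance, 26 v 26.** Twenty points of 26 is 5.2, so a gap of at least 6 patients is needed.

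| Prevalence | Independent binomials | Fixed margins (hypergeometric) |
|---|---|---|
| 30% | 9.5% | 13.2% |
| 40% | 11.9% | 8.9% |
| 50% | 12.6% | 16.5% |

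The fixed-margin column is uneven because the gap must have the same parity as the number of patients in the group (16, 21 or 26).

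**3. What an imbalance does to the hazard ratio.** Take 50% v 30% in the better group and a prognostic HR of 2. With no treatment effect, the ratio of average hazards is (0.5 × 0.5 + 0.5 × 1)/(0.3 × 0.5 + 0.7 × 1) = 0.75/0.85 = 0.88. On the log scale this is 0.125. The standard error at 40 events is 2/√40 = 0.316, so the shift is about 0.4 of a standard error. It is as likely to favour control as treatment.

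**4. Type I error.** The simulated unadjusted Cox test rejects in 4.8-5.6% of null trials, so there is no inflation.

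**5. Power, simulated** (52 patients, analysis at 40 events, conditional HR 0.4, 40% prevalence per factor).

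| Prognostic HR | One factor: unstratified v stratified | Two factors: unstratified v four strata |
|---|---|---|
| 1 (none) | 80% v 79% | 81% v 75% |
| 1.5 | 77% v 77% | 78% v 77% |
| 2 | 75% v 80% | 71% v 76% |
| 3 | 68% v 80% | 60% v 78% |

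With one factor, stratifying costs at most about 2 points when the factor is irrelevant, and gains 5 to 12 points when it is strong. With two factors and four strata, the cost is about 6 points if neither matters.

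**6. Alternative for a second factor.** In a separate simulation (44 patients, 40 events, two factors at 50% prevalence), a Cox model adjusted for both holds 78-79% power whatever their strength. Its likelihood-ratio test rejects in about 5.5-6.3% of null trials, so it suits a supportive analysis better than the primary test.

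**The case against.** Several stronger readings are tempting, and the documents do not support them.

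- **That randomization ignores these factors.** The algorithm is left open, not shown to omit them. Only the analysis text is plainly unstratified.
- **That first-line response groups also enter on different clocks.** Responders and stable disease share the same windows; only radiotherapy changes the timing.
- **That the protocol's background shows response to be prognostic here.** Section 2.1.2 says "The response rate in patients refractory to prior chemotherapy (6%) is lower than (37%) in those sensitive to first-line chemotherapy". That is response to topotecan in relapsed patients, not PFS by CR/PR against SD in patients who have not progressed.
- **That the radiotherapy wait exceeds the control median.** Eight weeks is 56/30.4 = 1.84 months, so at the lower limit it is about equal to 2 months, not longer.
- **That the stated 80% power is eroded.** This holds only if 0.4 is the HR within levels of the factor. The plan obtains 0.4 from the arm medians (2/5), which makes it a marginal HR. On that reading the unstratified test already has its planned power, and what is lost is the gain that adjustment would have brought.
- **That both factors should be crossed in a four-stratum log-rank test.** Step 5 shows this costs power unless the factors are strong.

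It is also fair to say that the imbalance effect is small beside the target effect: 0.125 against 0.916 on the log scale. All of these limits stand. They leave the omission itself, the later entry of radiotherapy patients, and a nearly free remedy.

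**Conclusion.** The point holds as a cheap improvement, not as a flaw that invalidates the design. The plan states no stratification factor and an unstratified primary analysis, although its own entry rules place post-chemotherapy radiotherapy patients on a later clock with a longer progression-free wait.

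In 52 patients a gap of 20 points or more in one such factor has a probability of about 9-13%, or up to about 16% with fixed margins. If the factor has a prognostic HR of 2 to 3 and 0.4 is conditional, power is about 68-75% unstratified against about 80% stratified on that factor. At a prognostic HR of 1.5 or below there is little or nothing to gain. False-positive risk is unaffected.

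Prevalence, prognostic strength and the 1:1 ratio are assumptions throughout. The documents give no figure for any of them, so no single corrected power can be stated.

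**What to change.** 1. State the allocation ratio and method in section 5.1.2, and stratify phase II randomization by post-chemotherapy radiotherapy (yes/no).
2. In section 11.3, make the primary log-rank test and Cox model stratified by that same factor.
3. Pre-specify a supportive Cox model that adds first-line response (CR/PR v SD) as a covariate. Do not use response to form a four-stratum log-rank test.
4. Before the stratum is defined, reconcile section 4.2.1.4 (at least 2 weeks from radiotherapy to randomization) with 4.2.1.5 and 5.1.2 (at least 8 weeks after post-chemotherapy radiotherapy). As written, it is unclear which patients each interval governs.

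Cost: two strata in the randomization system and a few lines of text. The statistical downside is about 2 points of power if radiotherapy turns out not to be prognostic.

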5.2 Drug Administration

5.2.1 $^{177}\text{Lu-DOTA}^0\text{-Tyr}^3\text{-Octreotate}$

$^{177}\text{Lu-DOTA}^0\text{-Tyr}^3\text{-Octreotate}$ will be administered every 8 weeks. The first dose of $^{177}\text{Lu-DOTA}^0\text{-Tyr}^3\text{-Octreotate}$ will be given two weeks after the first administration of nivolumab. Each dose is infused over 30 minutes. On the day of $^{177}\text{Lu-DOTA}^0\text{-Tyr}^3\text{-Octreotate}$ infusion, an intravenous bolus of anti-emetics will be given (suggested options: ondansetron (8 mg), granisetron (3 mg), or tropisetron (5 mg)). Administration of $^{177}\text{Lu-DOTA}^0\text{-Tyr}^3\text{-Octreotate}$ may be given one day earlier or delayed up to 1 week due to holidays, inclement weather, conflicts, or similar reasons. Prednisone should be avoided as preventive anti-emetic treatment due to potential-negative effect on anti-PD-1 therapy. In case of nausea or vomiting despite the use of aforementioned anti-emetic, patients can be treated with other anti-emetic medications at the discretion of the treating physician.

Concurrent amino acids are given with each dose of $^{177}\text{Lu-DOTA}^0\text{-Tyr}^3\text{-Octreotate}$ since co-infusion of amino acids leads to a significant reduction (47%) in the mean radiation dose to the kidneys. The amino acid solution and $^{177}\text{Lu-DOTA}^0\text{-Tyr}^3\text{-Octreotate}$ are administered in parallel by peripheral vein infusion.

Table 2. ¹⁷⁷Lu-DOTA⁰-Tyr³-Octreotate Administration Schedule.

Preparation	Starting time (h)	Infusion Rate (ml/h)	Duration (h)
Granisetron 3 mg (or alternative)	0	Bolus	-
Amino acids: 1-2.2 L solution*	0	250 to 550**	4
¹⁷⁷ Lu-DOTA ⁰ -Tyr ³ -Octreotate	0.5	50	0.5
Saline solution 25 mL – (two pump method) ¹	1	50	0.5

¹When the two-pump method is used, ¹⁷⁷Lu-DOTA⁰-Tyr³-Octreotate is pumped directly into the infusion line. The infusion line must be flushed with at least 25 ml of sodium chloride 9 mg/ml (0.9%) solution for injection after the infusion of ¹⁷⁷Lu-DOTA⁰-Tyr³-Octreotate.

* For specifications of the recommended commercial amino acid solution for coinfusion, please refer to the investigator brochure.

** The infusion rate may be reduced at the discretion of the investigator.

5.2.2 Nivolumab

Nivolumab will be administered once every 2 weeks until disease progression, patient withdrawal or toxicities. Nivolumab is administered intravenously and is administered first in combination studies. Wait 30 minutes before the next compound is administered (regardless of route of administration). Administer the infusion over 30 minutes (+/- 5 minutes) through an intravenous line containing a sterile, non-pyrogenic, low protein binding in-line filter (polyethersulfone with pore size of 0.2 micrometer to 1.2 micrometer). Do not coadminister other drugs through the same intravenous line. Nivolumab infusions are compatible with PVC or polyolefin containers and infusion sets, and glass bottles. Flush the intravenous line at end of infusion with appropriate amount of diluent (15-20 ml) to ensure that the total dose is administered. Administration of nivolumab may be given one day earlier or delayed up to 1 week due to holidays, inclement weather, conflicts, or similar reasons. The timing of subsequent administrations is then adjusted to maintain a 14 days-interval.

5.3 Dose Delays/Dose Modifications and Management of Toxicities Associated with ¹⁷⁷Lu-DOTA⁰-Tyr³-Octreotate and nivolumab

5.3.1 General Recommendations for Evaluation of Toxicities and Dose Delays/Modifications

Any patient who receives treatment on this protocol will be evaluable for toxicity. Toxicity will be assessed according to the NCI Common Toxicity Criteria for Adverse Events (CTCAE), version 4.03. Dose delays or dose modifications should be made according to the system showing the greatest degree of toxicity. Once the patient has a dose reduction due to toxicity, the dose will not

be re-escalated. Dose delays and dose modifications will be made using the following recommendations. At the discretion of the investigator, the study drugs may be held or dose modified independently if the observed AE is attributed to only one of the study drugs, while the patient continued to receive the drug not associated with the observed AE. For example, if the patient develops immune-related adverse events, nivolumab may be held following guidelines in section 5.3.5 while the patient continues to receive $^{177}\text{Lu-DOTA}^0\text{-Tyr}^3\text{-Octreotate}$. If the patient develops hematologic adverse events that are frequently associated with $^{177}\text{Lu-DOTA}^0\text{-Tyr}^3\text{-Octreotate}$, but rarely associated with nivolumab (e.g. thrombocytopenia), $^{177}\text{Lu-DOTA}^0\text{-Tyr}^3\text{-Octreotate}$ may be held while the patient continues on nivolumab. If the observed toxicity is attributable to both drugs, both drugs will be held.

Dose modifications for $^{177}\text{Lu-DOTA}^0\text{-Tyr}^3\text{-Octreotate}$ are permitted according to the table below.

Dose Level (DL)	$^{177}\text{Lu-DOTA}^0\text{-Tyr}^3\text{-Octreotate}$ (IV)
Level 1	3.7 GBq (100 mCi) every 8 weeks
Level 2	7.4 GBq (200 mCi) every 8 weeks

No dose modifications are allowed for nivolumab.

5.3.2 Hematologic Toxicities

Table 3. General Recommendations for Dose Modifications and Management of Hematological Toxicities

Adverse Event or Observation	Management
ANC* $\geq 1,000/\text{mm}^3$ AND Platelets** $\geq 75,000/\text{mm}^3$ AND Hemoglobin*** $\geq 8 \text{ g/dL}$	Maintain dose
ANC $< 1,000/\text{mm}^3$ OR Platelets $< 75,000/\text{mm}^3$ OR Hemoglobin $< 8 \text{ g/dL}$	On first occurrence, hold the drug(s) causing the toxicity up to 21 days until ANC $\geq 1,000/\text{mm}^3$, platelets $\geq 75,000/\text{mm}^3$, hemoglobin $\geq 9 \text{ g/dL}$. The subinvestigator and/or PI will determine whether one or both drugs are responsible for an observed toxicity and will initiate appropriate medical therapy and no change in dose upon re-initiation.

	
On second occurrence, hold the drug(s) causing the toxicity up to 21 days until ANC \geq 1,000/mm³, platelets \geq 75,000/mm³, hemoglobin \geq 9 g/dL. Treatment with ¹⁷⁷Lu-DOTA⁰-Tyr³-Octreotate may be restarted one dose level lower.
 
Patient who have not recovered to ANC \geq 1,000/mm³, platelets \geq 75,000/mm³, hemoglobin \geq 9 g/dL after 21 days should be removed from the drug causing the toxicity.

Grade 4 hematologic AE	
On first occurrence, hold the drug(s) causing the toxicity up to 21 days until ANC \geq 1,000/mm³, platelets \geq 75,000/mm³, hemoglobin \geq 9 g/dL. Treatment with ¹⁷⁷Lu-DOTA⁰-Tyr³-Octreotate may be restarted one dose level lower.
 
On second occurrence, discontinue the drug(s) causing the toxicity. Follow patient until resolution and/or stabilization of toxicity.
 
Patient who have not recovered to ANC \geq 1,000/mm³, platelets \geq 75,000/mm³, hemoglobin \geq 9 g/dL after 21 days should be removed from the drug causing the toxicity.

*ANC: Absolute neutrophil count. Growth factors to prevent neutropenia will not be administered prophylactically, but can be used during a drug hold to assist the recovery.

** Thrombocytopenia will be treated conservatively. In the absence of bleeding, or a necessary invasive procedure, platelet transfusions should be given for a platelet count \leq 10,000/mm³. If invasive procedure(s) is (are) planned, or the patient develops bleeding, platelet transfusions should be administered in accordance with the standard of practice, usually maintaining a platelet count above 50,000/mm³.

*** Red blood cell transfusion and is recommended if the hemoglobin falls below 8 g/dL or the patient is symptomatic. The initiation of erythropoietic therapy for the management of chemotherapy-induced anemia follows the American Society of Hematology/ASCO clinical practice guidelines (<http://www.asco.org>).

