5.0 TREATMENT PLAN

5.1 Treatment Dosage and Administration

5.1.1 Phase I

5.1.1.1 Dose Limiting Toxicity (DLT)

A DLT is defined as any toxicity not attributable to the disease or disease-related processes under investigation, which occurs from the first dose of study treatment (Day 1, Cycle 1) up to the last day of the cycle (Day 57). To be considered as DLT, it must be related to the study drugs (attributions: possible, probable, and definite) while fulfilling one of the following criteria as per the NCI Common Toxicity Criteria for Adverse Events (CTCAE) version 4.03:

- Toxicity grade 2 for platelets and any other grade 3 or 4 toxicity, excluding
 - Grade 3 diarrhea, nausea, or vomiting if it can be controlled with supportive therapy
 - Grade 3 endocrinopathy that is managed with or without systemic corticosteroid therapy and/or hormone replacement therapy and the patient is asymptomatic.
- Persistent (>21 days) non-hematologic grade 2 adverse events despite optimal medical management and treatment delay > 21 days
- Any other toxicity:
 - if worse than baseline value, documented, clinically relevant and/or unacceptable, and is judged to be a DLT by the investigators
 - if results in a protocol defined stopping criteria
 - if results in disruption of dosing schedule

Patients experiencing DLT will be monitored weekly until toxicity stabilization, and then every two weeks until normalization.

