5.3.3 Non-hematologic Toxicities

- The management of general AEs not otherwise specified in the following sections should be as per **Table 5**.
- Dose modifications for nausea, vomiting, and diarrhea will be made only if they are refractory to treatment. The time a given drug is held should not exceed 21 days.

Table 4. General Recommendations for Dose Modification and Management of Non-Hematological Toxicities

Observation	Management
-------------	------------

Grade 1 non-hematologic AE	Maintain dose level.
Any grade 2 non-hematologic AE related to study drug(s) lasting >7 days despite maximal intervention	Hold study drug(s)** for up to 21 days until toxicity resolves to ≤ grade 1. Treatment with ¹⁷⁷ Lu-DOTA ⁰ -Tyr ³ -Octreotate may be restarted one dose level lower.
Any ≥ grade 3 non-hematologic*	Hold study drug(s)** for up to 21 days until toxicity resolves to ≤ grade 1 or baseline. Treatment with ¹⁷⁷ Lu-DOTA ⁰ -Tyr ³ -Octreotate may be restarted one dose level lower.
Grade 3 or 4 non-hematologic AE related to drugs* that does not resolve to grade 1 or less within 21 days despite maximum supportive care after treating patient at the lowest reduced DL.	Remove patient from study regimen.

* Excluding 1) Grade 3 fatigue/asthenia < 2 weeks in duration, or grade 3 asymptomatic electrolytes imbalance with optimal and continuing repletion that downgrades to grade 1 or better within 7 days after onset of the event; 2) Grade 3 asymptomatic increase in gamma glutamyl transferase (GGT).

** For patients on combination therapy, if the observed AE is specifically attributed to only 1 of the drugs, that drug may be held while the patient continues to receive the drug not associated with the observed AE. The time a given drug is held should not exceed 21 days.

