5.3.4 Management of Infusion-Related Reactions

Table 5. Dose Modifications and Management of Infusion-Related Reactions

Observation	Management
Grade 1 or 2 AE	The infusion rate of study drug(s) may be decreased by 50% or temporarily interrupted until resolution of the event. Acetaminophen and/or antihistamines may be administered per institutional standard at the discretion of the investigator. Consider premedication prior to subsequent doses.
Grade 3 or 4 AE	Discontinue study drug(s). Manage severe infusion-related reactions (e.g., IM epinephrine, followed by IV diphenhydramine and ranitidine, and IV glucocorticoid).

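### Table 3 has overlapping rows for grade 4 hematologic events outside ANC, platelets and hemoglobin, and its recovery test is not tied to the count that triggered the hold

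*Combined protocol and SAP*

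**What the plan says.** Table 3 (section 5.3.2) has three rows.

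- **First row.** If ANC is at least 1,000/mm³, platelets at least 75,000/mm³ and hemoglobin at least 8 g/dL, the instruction is "Maintain dose". No exception is made for a grade 4 event in some other count.
- **Second row.** If any of the three falls below its limit, the causative drug is held for up to 21 days.
- **Third row.** The trigger is "Grade 4 hematologic AE", not limited to the three counts. The action starts "On first occurrence, hold the drug(s) causing the toxicity up to 21 days until ANC" and goes on to list the ANC, platelet and hemoglobin limits. After that, "Octreotate may be restarted one dose level lower". Then: "On second occurrence, discontinue the drug(s) causing the toxicity".

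The recovery limits in the second and third rows are the same: ANC 1,000/mm³, platelets 75,000/mm³, hemoglobin 9 g/dL. A patient who has not reached them after 21 days is to be taken off the causative drug.

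Section 5.3.3 begins "The management of general AEs not otherwise specified in the following sections should be as per" Table 5. That table is headed "Table 5. Dose Modifications and Management of Infusion-Related Reactions". The general non-hematologic table is Table 4, directly below the pointer.

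For phase I, section 5.1.1.1 counts as dose-limiting "Toxicity grade 2 for platelets and any other grade 3 or 4 toxicity, excluding" certain controllable gastrointestinal events and asymptomatic endocrinopathy. The event must be at least possibly drug-related and fall within cycle 1. No blood count is excepted.

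**The concern.** A management table should give one instruction for one set of laboratory values, and a hold should end when the problem that caused it has resolved. Table 3 fails on both points in cases the trial can observe, because section 6.2 requires a CBC with differential every two weeks on treatment. Two sites following the text could treat the same patient differently: one continues, the other holds and, at a second occurrence, discontinues. A patient could also lose a study drug because of a hemoglobin value that the same table accepts for continued dosing. Exposure, discontinuation and safety summaries would then partly reflect how each site read the table.

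**Working it through.** There is no stated figure to reproduce, because no sample size or error rate depends on these rules. The check applies the three rows literally. The individual counts below are illustrative; the limits are those of Table 3.

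**Inputs**

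- First row: ANC ≥ 1,000 and platelets ≥ 75,000 and hemoglobin ≥ 8.
- Second row: ANC < 1,000 or platelets < 75,000 or hemoglobin < 8.
- Third row: any grade 4 hematologic AE.
- Recovery, second and third rows alike: ANC ≥ 1,000, platelets ≥ 75,000, hemoglobin ≥ 9. The table separates these by commas; they are read here as all required.

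**Cases**

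| Case | Rows met | Recovery test |
|---|---|---|
| A. Grade 4 lymphopenia recorded as an AE; ANC 2,500, platelets 150,000, hemoglobin 10 | First (maintain) and third (hold) | Already met when the hold begins: 2,500 ≥ 1,000; 150,000 ≥ 75,000; 10 ≥ 9 |
| B. As A, but hemoglobin 8.5 | First (8.5 ≥ 8) and third | Not met, solely because 8.5 < 9 |
| C. Held for platelets below 75,000; platelets then recover to 150,000; ANC 2,500; hemoglobin steady at 8.5 | Second at the hold; first once platelets recover | Not met, solely because 8.5 < 9; off the causative drug after 21 days |
| D. Grade 3 lymphopenia; other counts as in A | First only | Not applicable |

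Case A gives two incompatible instructions. Even if the third row governs, the hold has no working end point: its recovery test does not look at the lymphocyte count and is satisfied at once. In case B the same event leads to a hold of up to 21 days, decided by a hemoglobin value unrelated to the trigger.

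Case C arises because only hemoglobin has a gap between the two limits. ANC: 1,000 − 1,000 = 0. Platelets: 75,000 − 75,000 = 0. Hemoglobin: 9 − 8 = 1 g/dL. Anyone held for ANC or platelets whose hemoglobin sits steadily in that 1 g/dL band cannot restart.

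Case D gives one instruction. If the event is drug-related and in cycle 1 of phase I, it is also a DLT under section 5.1.1.1.

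**Table pointer.** For a grade 3 or 4 event, Table 5 says discontinue. Table 4 says hold for up to 21 days and permits restart. Following the printed pointer therefore changes the action.

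**The case against.** Several points on the other side are sound.

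- **A low count is not automatically an AE.** Section 8.1.1 makes a laboratory abnormality an AE only under listed conditions, including the investigator's judgment of clinical impact. This narrows case A, but the conflict returns once the investigator makes that judgment.
- **Section 5.3.1 gives a precedence rule.** Modifications follow the system with the greatest toxicity. This leans towards the third row. It ranks systems, however, not two rows within one system, and it supplies no recovery criterion.
- **The third row may be meant for the three listed counts only.** That is possible, since its recovery test names only those, but the table does not say so.
- **The pointer looks like a numbering slip.** Section 5.1.1.2 cites Table 3 for the amino-acid infusion that appears in Table 2, and section 9.1.1 cites Table 10 for Table 9. That probably explains it; it still needs correcting.

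A reader might also infer more than the text supports.

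- *That the third row forces a dose cut.* It does not: the lower restart level is optional at first occurrence.
- *That one count must mean nothing, a dose cut or a DLT, as rival outcomes.* DLT status is a phase I, cycle 1 classification that depends on attribution and serves cohort decisions. It can coexist with any dosing action and may deliberately be stricter.
- *That hemoglobin limits of 8 and 9 contradict each other.* A restart limit above the hold limit is not itself an error, and section 4 requires more than 9 g/dL at entry. The difficulty is confined to patients held for another count.
- *That the effect on escalation can be quantified.* If drug-related grade 3 or 4 lymphopenia were the only DLT, with probability p, a level would pass with probability (1−p)³ + 3p(1−p)²·(1−p)³. Assuming p = 0.1 or 0.4 gives 0.906 or 0.309, hence stopping in 9% or 69%. Applying the row that accepts up to 2 of 6 at the highest level replaces the last factor by P(at most 1 of 3), and stopping falls to about 3% or 50%. The documents give no rate, and counting every event as drug-related is a further assumption. These figures are not evidence of an effect.

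**Conclusion.** The concern holds as a set of drafting defects in the management tables. Table 3 gives two instructions for a grade 4 hematologic AE outside its three counts. It provides no meaningful end to that hold, and it can remove a patient from a drug for a hemoglobin between 8 and 9 g/dL that never triggered a hold. Section 5.3.3 points to the wrong table, with a different action at grade 3 or 4. This rests on reading the three recovery limits as jointly required and the third-row trigger as covering any hematologic AE, which are the ordinary readings.

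How many patients would be affected cannot be derived from the documents: lymphopenia is never named, and the summary of clinical experience with the radioligand is redacted.

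The difference between the DLT definition and Table 3 at grade 3 (case D) is not an error in itself. It deserves the sponsor's confirmation because the recommended phase II dose is the phase I primary objective and section 11.2 expects it to be set from 9 to 12 patients, so the classification of a single count could affect a cohort decision.

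**What to change.** Reconcile the passages, leaving the clinical choices to the sponsor:

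1. State which Table 3 row governs hematologic AEs in counts other than ANC, platelets and hemoglobin, or state that the third row covers only those three.
2. Tie the recovery criterion to the count that triggered the hold.
3. Reconcile the hemoglobin limits for patients held for another count.
4. Correct the table pointer in section 5.3.3 and check the other table references.
5. Confirm in section 5.1.1.1 whether grade 3 or 4 events in counts outside Table 3's three are intended to be DLTs.

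The cost is wording and table edits in a protocol amendment, best made before the next cohort opens. No procedure or visit is added, because the differential count is already collected.
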